6.2.2.1 Group Phi

Assessment of reperfusion

At the receiving PCI hospital patients should be admitted to either the emergency department, coronary care unit or catheterisation laboratory (as per local practice) to assess reperfusion.

The patient's need for rescue coronary intervention will be assessed by both ECG and evaluation of clinical symptoms 90 min (or earlier if clinically indicated) after injection of tenecteplase. These patients may undergo coronary intervention immediately, if indicated, in accordance with the protocol criteria described below.

An additional ECG should be taken before starting the procedure. If there are clinical or electrocardiographic signs of reperfusion that have occurred after the previous ECG, the planned coronary intervention may be postponed.

Cardiac Catheterisation

- If ST-segment resolution is $\geq 50\%$ in the qualifying lead (that had the maximum initial ST-segment elevation in the baseline ECG), diagnostic coronary angiography (followed by

elective PCI +/- stenting, if indicated) should be performed no sooner than 6 hours, but within 24 hours after administration of tenecteplase. This will be considered as planned catheterisation according to protocol

- If ST-segment resolution is < 50 % relative to the ST-segment elevation in the qualifying lead at baseline, irrespective of the presence or absence of clinical symptoms, rescue coronary intervention should be performed promptly.
- If any of the following indications require coronary intervention (irrespective of previous ST-segment resolution), urgent coronary intervention is indicated at any time:
 - haemodynamic instability (presence of any of the following requiring inotropic support: sustained hypotension, cardiogenic shock, or congestive heart failure)
 - refractory ventricular arrhythmias requiring cardioversion or pharmacological treatment
 - worsening ischaemia
 - progressive or sustained ST-segment elevation which, in the judgement of the investigator, requires immediate coronary intervention

All rescue and urgent coronary interventions will be adjudicated by an independent clinical expert as previously described.¹⁹ Feedback to participating sites regarding adherence to protocol defined indications for rescue will be provided as appropriate.

Further ECG measurements

Further ECG measurements are listed in Table 4.

Table 4: Overview of ECG measurements in Group PhI

Timing of ECG	Location	Reason for ECG
Baseline	Pre-PCI hospital: on site/ambulance/ER community hospital	ECG for assessment of STEMI entry criteria
90 min after bolus tenecteplase or earlier if indicated	In-PCI hospital: emergency dept. or CCU	Assessment of reperfusion
In case of catheterisation (with or without PCI/stenting) or rescue or urgent PCI, respectively: - immediately before - and 30 min after the end of the procedure.	In-PCI hospital: catheter laboratory	Re-assessment of reperfusion

Timing of ECG	Location	Reason for ECG
Any time, if indicated (serial ECGs)	In-PCI hospital	Verification of ischaemia or reinfarction
At 4 days or hospital discharge whichever comes first	In-PCI hospital	Assessment infarct size using QRS score

Collection of data

During the patient's stay in hospital (i.e., until and including the day of discharge) the following data will be collected:

- Concomitant therapy
- Troponin I/T (CK/CK-MB) 8-12 hrs and 24 hrs after randomisation, respectively, and also at any time in case of signs and symptoms suggestive of recurrent myocardial ischaemia or reinfarction
- 12-lead ECG (please refer to Table 4)
- Data on catheterisation/coronary intervention(s)
- TIMI flow grade (before PCI and at the end of the angiographic procedure)
- Any occurrence of adverse events, and serious adverse events/serious clinical events

The following assessments will be performed on the **day of discharge from hospital** (or transfer to a rehabilitation centre or nursing home)

- Blood test for haematology as per hospital routine
- 12-lead ECG (cf. Table 4)
- Any occurrence of adverse events, and serious adverse events/serious clinical events

6.2.2.2 Group PPCI

Patients randomized to PPCI will receive medical treatment before, during and after PPCI according to established local standards. Additional GP IIb/IIIa antagonists may be given at the investigator's discretion.

During the in-hospital period several 12-lead ECGs will be taken as summarised in Table 5.

Table 5: Overview of ECG measurements in PPCI Group C

Timing of ECG	Location	Reason for ECG
Baseline	Pre-hospital: on site/ambulance/ER community hospital	ECG for assessment of STEMI entry criteria

Timing of ECG	Location	Reason for ECG
Immediately prior to PCI after arrival in PCI hospital	In-PCI hospital: catheter laboratory	Assessment of pre-PCI patency
30 min after the end of the intervention	In-PCI hospital	Reassessment of reperfusion
Any time, if indicated (serial ECGs)	In-PCI hospital	Verification of ischaemia or reinfarction
At 4 days or hospital discharge whichever comes first	In-PCI hospital	QRS score for infarct size

During the patient's stay in hospital, data on PPCI will be collected. All further assessments during the initial hospitalisation and prior to the patient's discharge from hospital (or transferral to a rehabilitation centre or nursing home) are identical to those assessed in Group PhI (please refer to the above paragraph, 6.2.2.1).

6.2.3 End of trial and follow-up period

6.2.3.1 End of trial (day 30)

The end-of-trial visit will take place at day 30. Data may however be collected until and including day 37. If a visit at the outpatient clinic is not possible the patients may be contacted by phone. The following data will be collected:

- Data on any rehospitalisation occurring after hospital discharge up to (including) day 30
- Any occurrence of adverse events, and serious adverse events/serious clinical events since hospital discharge or (if the patient is still hospitalised) that have not yet been recorded

6.2.3.2 Follow-up

Data for the 1-year follow up should be collected at day 365 (up to and including day 395). The required evaluations may be assessed via phone (if a physical visit is not performed) or can also be obtained from medical records.

The following data will be collected at 1-year: vital status/all-cause mortality and rehospitalisation for cardiovascular reasons (since day 30).

6.3 REMOVAL OF PATIENTS FROM THERAPY ASSESSMENT

As soon as the patient is randomised, the patient is considered a trial participant irrespective of

whether he or she received any trial-specific treatment or not.

A patient may withdraw from the trial at any time without the need to justify the decision.

In case of withdrawal all data collected until (and including) the day of withdrawal will be kept in the trial database. Furthermore vital status at 30 days and 1 year will be collected.

7. STATISTICAL METHODS AND DETERMINATION OF SAMPLE SIZE

7.1 STATISTICAL DESIGN/MODEL

The trial is a prospective, multi-centre, international, randomised (2:1), open-label, parallel-group comparison, conducted for investigating the efficacy and safety of

- A. Study treatment (Group PhI)
- B. Primary PCI according to local standards (Group PPCI)

in patients with acute myocardial infarction randomised < 3 hours from symptom onset.

The principal aim of the trial is to evaluate the safety and efficacy in the 2 treatment groups measured by ST segment resolution, TIMI flow grades, and clinical events as listed in section 2.1.

7.2 PLANNED ANALYSES

Baseline characteristics will be tabulated and differences among the two treatment groups will be examined by means of descriptive statistics.

The primary analysis is an intent-to-treat analysis of all randomised patients. Patients will be analysed according to the treatment group to which they were randomised, irrespective of which study drug was given or if any study drug was received.

7.2.1 Interim analyses

After 50 % of the planned recruitment a formal interim analysis will be performed by the Data and Safety Monitoring Board (DSMB) to evaluate and advise the Executive Committee on the feasibility of enlarging the sample size and to turn the study into a confirmatory trial. Continuous safety monitoring will be done by the DSMB with particular emphasis on the incidence of systemic bleeding and intracranial haemorrhage (ICH); details are documented in the DSMB charter.

7.3 HANDLING OF MISSING DATA

No imputation of missing data is foreseen. Best efforts will be made to collect complete data for the clinical events of interest. Distribution of the missing data will be checked across groups.

7.4 RANDOMISATION

The randomisation will be stratified by centre and, within the centres, performed in blocks to ensure balanced distribution of the treatment groups at any time. Randomisation will be available daily for 24 hours via a centralised telephone Interactive Voice Response System (IVRS) or web randomization. Each site (ambulance/ER of community hospital) will be provided with a telephone number and a PIN code that will connect them to a computerised script identifying the treatment group. For details on the use of IVRS see the manual in the Investigator Site File.

Patients are considered randomised as soon as the treatment group has been assigned.

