3.3 SELECTION OF TRIAL POPULATION

Patients with ST-elevation acute myocardial infarction (STEMI) within 3 hours of symptom onset in the pre-hospital setting will be randomised to Group PhI for a strategy of early pre-hospital/ER community hospital fibrinolysis or to PPCI, if the eligibility criteria mentioned below are met.

Approximately 600 patients (400 patients to group PhI and 200 patients to group PPCI) will be enrolled in approximately 65 sites located in different countries (for sample size calculation see section 7). A minimum of 100 patients \geq 70 years of age will be randomized to the PhI arm

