4.1.2 Methods of assigning patients to treatment groups

Immediately after screening in the pre-hospital setting, eligible patients will be randomised 2:1 to the pharmaco-invasive therapy or to PPCI.

Randomisation will be performed centrally by means of an interactive voice response system (IVRS), which has to be called by the investigator or an authorised member of site staff.

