7.5 DETERMINATION OF SAMPLE SIZE

As mentioned before this is a hypothesis generating trial. No primary hypothesis or primary endpoint have been formulated. Approximately 600 patients are planned to be randomized with 400 receiving PhI therapy and 200 PPCI. A minimum of approximately 100 patients \geq 70 years of age will be randomized to the PhI arm. The aim is to combine ECG and angiographic data from the latter group with similar data from STREAM-1^{16, 18} in order to have a more reliable estimate of the efficacy of the PhI strategy in elderly patients. The analysis of ECG data, angiographic data and clinical events will be described in detail in the statistical analysis plan. Although the study of 600 patients is not powered to show a difference in clinical events, given the elderly nature of the population there will be ample efficacy and safety events to observe. They will be reported along with their 95% confidence limits. For reference, in patients \geq 60 years from STREAM-1 the 30 day composite of death, shock, heart failure and re-MI ranged between 18 and 20 % for PhI and PPCI groups. Bleeding data in this age group were 1.7 % and 0 % ICH and 8.8 % and 7 % non-intracranial major bleeding respectively. If the study would turn into a confirmatory trial after the interim analysis a primary hypothesis on a combined clinical endpoint will be pre-specified.

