### **8.5 Efficacy endpoints of primary interest**

#### **8.5.1 Clinical endpoint**

The primary efficacy endpoint will be analysed by presenting the event rates and the 95% confidence intervals (two-sided) separately for each treatment group. In addition, the two treatment groups will be compared using a working Poisson regression model (Zhou (2004)) from which the between-group comparison will be estimated by means of a relative risk with a 95% confidence interval (two-sided).

In case there are no events in a particular treatment group (before imputation), an artificial observation in each cell (treatment group by event) with weight 0.5 will be added in order to estimate the relative risk.

Furthermore, the risk difference with a 95% confidence interval will be calculated using PROC FREQ.

Standard multiple imputation methodology as described in Section 8.1 will be applied to combine the results over the different multiple imputations, if applicable.

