## **8.9 Other Endpoints**

### **8.9.1 Within 30-days**

Duration of index hospitalization will be compared between treatment groups by means of a t-test or Wilcoxon rank test, whichever is appropriate. The duration in each treatment group will be described using means and standard deviations, or median and interquartile range, whichever is appropriate.

The mean difference or Hodges-Lehman estimator with a 95% confidence interval will be reported, whichever is appropriate..

Patient still in hospital at day 30 will be analysed as 30 days. The proportion of patients still in hospital at 30 days will be reported.

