### **9.1.4 Angiographic endpoints**

#### **9.1.4.1 TIMI flow at first coronary angiography**

The TIMI flow at first coronary angiography will be compared between treatment groups by means of a stratified trend test, i.e. the VanElteren test in which is stratified on study. In addition, the combined numbers and percentages will be reported.

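### Randomisation is stratified by centre but no SAP analysis uses centre; if sites differ, the length-of-stay interval and the TIMI-flow test are conservative, and centre-stratified versions are a cheap improvement

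*Protocol*

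**What the plan says.** Protocol 7.4 sets the allocation: "The randomisation will be stratified by centre and, within the centres, performed in blocks". The stratum is the enrolling unit: "Each site (ambulance/ER of community hospital) will be provided with a telephone number". Protocol 4.1.2 gives the ratio: "eligible patients will be randomised 2:1 to the pharmaco-invasive therapy or to PPCI". Protocol 3.3 says patients "will be enrolled in approximately 65 sites located in different countries", and Protocol 7.5 gives the size: "Approximately 600 patients are planned to be randomized with 400 receiving PhI therapy and 200 PPCI". The block size is not stated.

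The between-arm analyses in the SAP are all unstratified within STREAM-2:

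- **Composite, and the binary endpoints that refer back to it (8.5.1):** "the two treatment groups will be compared using a working Poisson regression model", plus a risk difference from PROC FREQ.
- **TIMI flow (8.5.4):** Cochran-Armitage trend test. Table 10.1.3 shows counts and a p-value only.
- **Length of stay (8.9.1):** "Duration of index hospitalization will be compared between treatment groups by means of a t-test or Wilcoxon rank test", with a mean difference or Hodges-Lehmann estimate and its 95% interval.
- **One-year rehospitalisation (8.9.2):** Gray's test, no stratum stated.

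Centre is also absent from the imputation covariates (SAP 5) and the subgroup list (SAP 8.11). Both contain only the place of randomisation, ambulance or community hospital. The pooled elderly analyses do stratify, but by trial: "i.e. the VanElteren test in which is stratified on study" (SAP 9.1.4.1). The SAP gives no reason for leaving centre out.

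**The concern.** Blocking within centre balances the arms within each centre, so differences between centres largely cancel out of the treatment comparison. An unstratified t-test, Wilcoxon test or trend test still counts that variation as noise. Its error term can therefore be larger than the real error.

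Two endpoints are the natural candidates. Length of stay depends on local discharge and transfer habits (Protocol 5.3.1). TIMI flow is graded by the local investigator (Protocol 5.2.1, SAP 6.1.4) and is one of the efficacy endpoints of primary interest. What is at stake is precision for length of stay and sensitivity of the TIMI-flow test.

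**Working it through.** **Inputs from the documents.** 600 patients at 2:1, so 600 × 2/3 = 400 and 200, which agrees with Protocol 7.5. About 65 sites, so 600/65 = 9.2 patients per site. The documents state no power, precision or ICC, so there is no planned figure to reproduce.

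**Assumptions.** ICC from 0 to 0.30, blocks of 3 or 6, equal or skewed site sizes. Simulated length of stay is right-skewed and capped at 30 days, with the ICC on the log scale. TIMI flow is a three-level score cut from an underlying normal variable that carries the ICC.

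**Step 1: formula under full balance within centres.** The true variance of the arm difference is (1 − ICC) × σ² × (1/n₁ + 1/n₂). The unstratified analysis uses σ² × (1/n₁ + 1/n₂). So the unstratified SE divided by the true SE is 1/√(1 − ICC), and the actual two-sided level of a nominal 5% test is 2 × [1 − Φ(1.96/√(1 − ICC))].

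**Step 2: simulation under no treatment effect,** 3,000 trials per setting (Monte Carlo error on the level about √(0.05 × 0.95/3000) = 0.004). Ranges run over block size and site-size pattern. The simulated SE excess is for a continuous outcome.

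| ICC | SE ratio, formula | Level, formula | SE excess, simulated | Wilcoxon level, length of stay | Cochran-Armitage level, TIMI |
|---|---|---|---|---|---|
| 0.05 | 1.026 | 0.044 | 0–4% | 0.044–0.051 | 0.043–0.049 |
| 0.10 | 1.054 | 0.039 | 3–6% | 0.037–0.041 | 0.040–0.047 |
| 0.20 | 1.118 | 0.028 | 9–11% | 0.030–0.033 | 0.037–0.040 |
| 0.30 | 1.195 | 0.019 | 16–18% | 0.021–0.025 | 0.026–0.036 |

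A centre-stratified rank test on length of stay had a level of 0.044 to 0.056 at every ICC from 0 to 0.30.

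**Step 3: gain in interval width for a continuous outcome.** With incomplete blocks in small sites, stratifying costs about 1 to 1.5% of width when centres do not differ. Taking 1.25% as the midpoint, stratified width over unstratified width is roughly 1.0125 × √(1 − ICC):

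- ICC 0.05: 1.0125 × 0.975 = 0.987, about 1% narrower
- ICC 0.10: 1.0125 × 0.949 = 0.961, about 4% narrower
- ICC 0.20: 1.0125 × 0.894 = 0.906, about 9% narrower
- ICC 0.30: 1.0125 × 0.837 = 0.847, about 15% narrower

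Direct simulation with 65 unequal sites gives the same 1%, 4%, 9% and 15%.

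**Step 4: which unit clusters.** The strata are ambulance or community-hospital sites, while angiography takes place at the PCI hospital and the stay is counted from admission there. If each site feeds two PCI hospitals rather than one, the simulated narrowing falls to about 0–1%, 1–2%, 3–4% and 6–7% at the same ICCs.

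**Step 5: the composite.** At 19%, the midpoint of the 18 to 20% in Protocol 7.5, the SE of the risk difference is √[0.19 × 0.81 × (1/400 + 1/200)] = 0.0340, so the 95% half-width is 1.96 × 3.40 = 6.66 percentage points. A centre-stratified Mantel-Haenszel risk difference changes the width by +1.0 to +1.5% if centres do not differ, −0.3 to −1% at a between-centre SD of 0.5 on the logit scale, −2 to −3% at 0.7 and −5 to −6% at 1.0. Up to an SD of 0.7, the half-width stays between 6.66 × 0.97 = 6.46 and 6.66 × 1.015 = 6.76 points. For the relative risk, a centre-stratified Mantel-Haenszel estimate changes the SE of the log relative risk by +1.5% to −2.6% for SDs from 0 to 0.7, and its true sampling SD is 0.4 to 2.5% larger than that of the unadjusted estimate.

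**The case against.** The best case for leaving the SAP alone has four parts.

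- **The size is assumed.** No ICC appears in either document, and at 0.05 or below the effect is barely visible. This stands. It rules out the reading that the planned standard errors are in fact too wide; they are too wide only if sites differ.
- **The stratum may not be the unit that clusters.** Discharge practice and TIMI grading belong largely to the PCI hospital. The documents do not say whether a site feeds one such hospital or several. This also stands, and it can cut the gain by half or more.
- **Little depends on it.** The trial is exploratory with descriptive p-values (Protocol 2.2, SAP 2), the error is conservative, and length of stay sits under Other Endpoints. A reader might infer that the inference is invalid or that false positives are inflated. The documents do not support that: the actual level falls below 5%.
- **Centre-stratifying everything would be a poor trade.** A reader might infer that the composite relative risk should also become a centre-stratified Mantel-Haenszel estimate. Step 5 shows no real gain in precision. With about 9 patients per site and a 19% event rate, about a third of centres would contribute nothing. It would also change the estimator for every binary endpoint that refers to SAP 8.5.1. The stratification by study in SAP 9 combines two trials and is no precedent for 65 small strata.

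None of this removes the narrower point. For length of stay and TIMI flow, the analysis can follow the randomisation at a cost of at most about 1.5% in interval width.

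**Conclusion.** The point holds as a minor, conditional improvement. Randomisation is stratified by centre and no described SAP analysis uses centre; that part is plain from the documents. The consequence is conservatism if outcomes vary between randomising sites.

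For length of stay, the 95% interval could be about 1% to 15% narrower for ICCs of 0.05 to 0.3 if each site feeds one PCI hospital, and about 0 to 7% narrower if each feeds two. It would be about 1 to 1.5% wider if centres do not differ. For TIMI flow no SE or interval is reported, so the effect is only a slightly conservative test: level 0.037 to 0.040 at an ICC of 0.20. The composite is essentially unaffected unless centres differ very strongly. The figures also assume blocks of 3 or 6 and the outcome shapes given above.

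**What to change.** - **SAP 8.9.1:** compare length of stay with a centre-stratified test (van Elteren, or a within-centre model). Report a centre-aligned Hodges-Lehmann difference or a within-centre mean difference with its 95% interval.
- **SAP 8.5.4:** replace the Cochran-Armitage test with a centre-stratified trend test (van Elteren or Cochran-Mantel-Haenszel mean score), for both first and last angiography.
- **Small sites:** pre-specify a rule for merging very small sites, for example within country. Since the documents do not state the block size, define the rule by patient numbers or by both arms being present.
- **Sensitivity:** keep the currently planned unstratified results alongside.
- **SAP 8.5.1:** leave the working Poisson relative risk as the main analysis of the binary endpoints. A centre-stratified risk difference there is optional.

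The cost is SAP wording, some extra programming (mainly for the aligned Hodges-Lehmann interval), and an interval up to about 1.5% wider if centres do not differ. Trial conduct and data collection do not change.

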7.5 DETERMINATION OF SAMPLE SIZE

As mentioned before this is a hypothesis generating trial. No primary hypothesis or primary endpoint have been formulated. Approximately 600 patients are planned to be randomized with 400 receiving PhI therapy and 200 PPCI. A minimum of approximately 100 patients \geq 70 years of age will be randomized to the PhI arm. The aim is to combine ECG and angiographic data from the latter group with similar data from STREAM-1^{16, 18} in order to have a more reliable estimate of the efficacy of the PhI strategy in elderly patients. The analysis of ECG data, angiographic data and clinical events will be described in detail in the statistical analysis plan. Although the study of 600 patients is not powered to show a difference in clinical events, given the elderly nature of the population there will be ample efficacy and safety events to observe. They will be reported along with their 95% confidence limits. For reference, in patients \geq 60 years from STREAM-1 the 30 day composite of death, shock, heart failure and re-MI ranged between 18 and 20 % for PhI and PPCI groups. Bleeding data in this age group were 1.7 % and 0 % ICH and 8.8 % and 7 % non-intracranial major bleeding respectively. If the study would turn into a confirmatory trial after the interim analysis a primary hypothesis on a combined clinical endpoint will be pre-specified.

